Effects of a walking program and inspiratory muscle training

**Effects of a Walking Program and Inspiratory Muscle Training
on Individuals with Chronic Heart Failure**

(ClinicalTrials.gov identifier :NCT01560871)

12/2/2013

Protocol Title

Effects of a walking program and inspiratory muscle training on individuals with chronic heart failure - a pilot study

1) Investigator

[name], PT, PhD

2) Objectives

The purpose of this pilot study is to examine the effects of inspiratory muscle training (IMT) plus home-based walking program in individuals with chronic heart failure. The primary outcomes are: respiratory muscle strength as indicated by maximal inspiratory pressure (P_Imax), cardiovascular endurance (indicated by the six-minute walk test distance), autonomic function (indicated by the heart rate variability) and health-related quality of life. We hypothesize that both groups will have improvements in P_Imax, cardiovascular endurance, heart rate variability, and quality of life, and that the extent of improvements will be greater for the experimental group (high-intensity IMT) than the sham group (low-intensity IMT). We plan to recruit patients who are discharged within 6 months after acute illness, since these patients may be medically stable and mobility independent, but their overall exercise capacity may not be ready for full function in the community yet.

3) Background

Prevalence of heart failure is approximately 1% ^[1]. The leading causes of heart failure are coronary artery disease, hypertension and diabetes. Other causes include cardiomyopathy, heart valve disease, arrhythmia and congenital heart disease. Patients often develop symptoms when all compensatory mechanisms fail to provide adequate cardiac output of the heart. General fatigue and dyspnea with exercises often reduce their desire for physical activity. Deconditioning and dyspnea eventually becomes a vicious cycle. Health care cost for patients with heart failure is skyrocketing due to its repetitive, costly, and prolonged hospitalization. ^[2] With an increasing elderly population, it is estimated that the burden of care would continue to increase for heart failure.

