- iii) It will be emphasized that their participation in the study is completely voluntary, and it will not affect their medical treatments in any ways.
- iv) Participants will be paid a total of \$50.

- v) A total of 30 subjects will be enrolled from the Presbyterian Hospital of Dallas, excluding screening failure.

b) Inclusion and Exclusion Criteria

- i) Subjects inclusion criteria:
 - (1) adults with chronic heart failure (NYHA Functional Class II-III) who are just discharged from an acute care hospital in the past three months,
 - (2) with BMI < 35 kg/m²,
 - (3) greater than 18 years of age,
 - (4) walk independently with or without assistive device.
(note: According to New York Heart Association's Functional Classification, patients who have reasonable compensatory ventricle remodeling and relatively normal cardiac output at rest and with inadequate increase in cardiac output upon exertion belong to Class II and III, whereas those with inadequate cardiac output at rest will be classified as NYHA Class IV.)
- ii) The total expected number of subjects needed to complete the study is 50 excluding those screen failure. Thirty subjects will be recruited from the Presbyterian Hospital of Dallas.

c) Study Endpoints

- i) The primary study endpoint will be that 30 participants complete all evaluations, reassessment, and 6-week of training program. The secondary study endpoint would be all data management is completed.
- ii) The primary safety endpoint would be that participants complete all study protocols without adverse responses. The secondary safety endpoint could be all research data get kept and protected 10 years accordingly.

d) Procedures involved in the Human Research

- i) This study will be a double-blind randomized controlled study. Evaluators will not be aware of subject's group assignment. Each subject does not know group assignment either
- ii) Timeline of the procedures
 - (1) Recruitment: Two research coordinators screen medical charts to identify potential subjects
 - (2) initial evaluation
 - (a) History taking
 - (b) set up ECG electrodes on the holter monitor unit to monitor heart rhythm throughout the session,
 - (c) maximal inspiratory muscle strength test (P_{Imax})
 - (d) Grip strength test
 - (e) 2-min comfortable walking speed test
 - (f) single limb stance test at eyes open and eyes closed conditions
 - (g) rest for 15 minutes (supine – standing - supine, 5 min each)

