Since most individuals with heart failure are older than 50 years of age, so we include 3 outcomes specific to older people. (1) Grip strength: A dynamometer for grip strength will be used for 3 trials. (2) Single limb stance test at both eyes open and eyes closed conditions. The time to maintain single limb stance will be recorded for 3 trials at both conditions. (3) Comfortable speed: the participant will be asked to walk at their comfortable speed back and forth over a 44-foot segment of hallway for two minutes. The times for completing the 44-foot distance will be measured. Heart rate variability will be recorded during the above 3 outcome measures. After these measures, the participant will rest for 15 minutes in the following positions: supine (5 min), standing (5 min), then in supine again (5 min). The holter monitor will continue to monitor their heart rate activity when resting in these 3 positions.

After rest, we will set up telemetry ECG system and administer the six-minute walk test. The participant will be instructed to walk for 6 minutes and to cover as much distance as they can. The distance walked, symptoms and signs of exercise intolerance will be monitored and recorded. After the first trial, the participant will be

allowed to rest for about 15 minutes to allow heart rate returns to initial baseline (+/- 5 beats). During this rest period, we will have the participant fill out the 2 questionnaires (Minnesota Living with Heart Failure Questionnaire and SF36 Questionnaire). Then, we will repeat the six-minute walk test to account for learning effect. The SF-36 questionnaire asks a question regarding sexual difficulties. Subjects can refuse to answer if they find it uncomfortable.

All the initial outcome evaluations will be repeated after 6 weeks. There will be two research team members doing the evaluations and another two research team members conduct the weekly re-assessment.

Each participant will be unknowingly assigned to one of the two groups: (1) a walking program with a sham (low-intensity) Inspiratory Muscle Training (IMT) protocol, and (2) a walking program with a real (high intensity) IMT at 60% of maximal inspiratory pressure (P_Imax). Research team members who conduct evaluations will be blinded to the group assigned. Only the primary investigator and those research members who conduct the weekly re-assessment of P_Imax know the group assignment.

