Each participant will be given an accelerometer to track their 7-day physical activity for the first and the last week of training. The home-based walking program will consist of walking at an intensity of “somewhat hard” to “hard” on the Rating of Perceived Exertion (RPE) scale. Participants will be educated on the 10-point RPE scale to judge their fatigue level. For example, at rest, they would rate their exertion level as “nothing at all” which is equivalent to “zero” on the RPE scale. If they were very tired and shortness of breath after any exhausted activities such as climbing two to three flights of stairs, they probably rate their exertion level as “very, very, very hard.” The scale has been shown to be highly related to a person’s heart rate. They will be advised to slow down if they feel their exertion level is toward the “very hard” level. Participants will begin walking at least 15 minutes twice a day, or as tolerated, for 7 days a week and eventually progress to 45-50 minutes a day by six weeks. They will also be instructed to wear a simple pedometer each day to record step counts. During their weekly re-assessment visit, a research team member will calculate the “mean” and “standard deviation” of their previous 7-day step counts. They are encouraged to reach the mean step counts for the following week; however, if they are tired on a specific day, they are encouraged to at least reach the lower target (e.g., the mean minus one standard deviation of previous week’s step counts). We found this approach to be effective based on a case study.

For the IMT, the training threshold will be set at 60% of P_Imax (maximal inspiratory pressure) for the experimental group. The participant will perform the breathing exercise one session daily with a nose clip used, so the participant breathes completely through the mouth. The 6 Interval Levels: (6 inspiratory efforts in each level): (1) 60s rest interval; (2) 45s rest interval; (3) 30s rest interval; (4) 15s rest interval; (5) 10s rest interval; (6) 5s rest interval, trained to exhaustion. The sham IMT group will be trained at fixed 15% P_Imax which is lower than the training threshold

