(i.e., 30% P_Imax) reported in the literature. The time commitment for their IMT exercise is about 15-20 minutes per day for both groups. Each participant will have weekly follow up visit which can be done either at our facility or a research team member will do a home visit for about 15 to 20 minutes to reassess their new P_Imax and reset the new IMT intensity for the following week. In addition, the research team will record their ambulatory activity of the previous week.

Study will be conducted in the research suite (8th floor) at the T. Boone Pickens Institute of Health Sciences – Dallas of TWU. There will be no other personnel in the area except the research team members. The weekly sessions for reassessment of respiratory muscle strength will be conducted in the research suite on TWU-Dallas campus, at the outpatient heart failure clinic of the PHD, or at the patient's home whichever is convenient for the participant.

e) Data management

- i) The PI, research coordinators, and research graduate assistants will be responsible for data collection and transmission of data.
- ii) No specimens will be collected.
- iii) Data will be transferred from the hard copies of data collection forms to the password protected computer for further data management with Excel program and SPSS statistical software.
- iv) Only subjects' initials and other study related findings will be record in the data forms. During data management, only codes will be used. For example, each participant will be coded as "group number + subject number" (e.g., C-1 (control group, subject 1); E-1 (experimental group-subject 1)). An excel file containing the master list of subjects' initials and codes will be kept in a password protected computer. The data will be stored in a locked cabinet at Room 5610, School of Physical Therapy of the TWU- Dallas campus. Only the research team members have access to the data. All data will be coded. The data will be stored for 10 years after completion of the study and it will be destroyed after 8/31/2023.
- v) Data Analysis: Two-way (group x time) repeated measure ANOVA (or multivariate ANOVA) will be used to compare the primary and secondary outcome measures between the 2 groups (sham IMT vs. real IMT) and across the 2 time points (pre- vs. post-training). The PI will consult a statistical consultant for final data analysis in the future.

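### Optional precision gain: adding ANCOVA on the baseline value to the two-time-point group-by-time ANOVA in section 6(e)(v) would usually sharpen the IMT comparison at almost no cost

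*Combined protocol and SAP*

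**What the plan says.** Section 6(e)(v) holds the whole analysis plan: "Two-way (group x time) repeated measure ANOVA (or multivariate ANOVA) will be used to compare the primary and secondary outcome measures", between sham and real IMT and across a pre- and a post-training time point. It names no covariate, and no baseline adjustment appears elsewhere. The section ends: "The PI will consult a statistical consultant for final data analysis in the future".

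Section 2 states two hypotheses. One is that both groups will improve. The other is that "the extent of improvements will be greater for the experimental group (high-intensity IMT) than the sham group (low-intensity IMT".

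What a baseline-adjusted analysis needs is already planned. Section 6(d)(i) says "This study will be a double-blind randomized controlled study", and section 6(d)(iii) says "All the initial outcome evaluations will be repeated after 6 weeks". One measure lacks a pre-training value: "Each participant will be given an accelerometer to track their 7-day physical activity for the first and the last week of training".

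**The concern.** With two time points, the interaction compares mean change between groups, which fixes the coefficient on baseline at 1. ANCOVA estimates that coefficient from the data. Under randomization both methods target the same IMT effect, but subtracting the full baseline value adds noise when the pre-post correlation is modest.

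Chance imbalance shows this at the planned size. With 15 per group, the between-group difference in baseline means has a standard deviation of sqrt(2/15) = 0.37 pre-training SDs. At rho 0.5 with equal SDs, an imbalance of that size moves the change-score estimate by (1 − 0.5) × 0.37 = 0.18 SD. ANCOVA adjusts for it. This is the same precision gain seen another way, not a claim of bias.

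At stake is the width of the confidence interval for the IMT effect in a pilot of 15 to 25 per group.

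**Working it through.** **Inputs from the protocol.** Two groups and two time points (6(e)(v)). From 6(e)(vii): 15 per group for 80% power, about 25 per group enrolled, a P_Imax SMD of 1.3605 (lower limit 1.0510), and a lower limit of 0.8416 for functional capacity.

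**Assumptions, because the documents are silent.** rho from 0.3 to 0.9; k = post SD / pre SD from 0.9 to 1.25; two-sided alpha 0.05; n = completers per group.

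**The plan's own figure.** Alpha and the design effect size are not stated, so 15 per group cannot be reproduced uniquely. The normal approximation n = 2(1.96 + 0.842)²/d² gives 8.5, so 9, at d = 1.3605, and 14.2, so 15, at d = 1.0510. The point below does not depend on which was used.

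**Equivalence.** On a generated data set with 15 per group, the interaction F and the squared t for change were both 3.8156.

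**Variances** (pre SD = 1):
- Interaction: (1 + k² − 2·rho·k)·2/n, with 2n − 2 df.
- ANCOVA, averaged over chance baseline imbalance: k²(1 − rho²)·(2/n)·[1 + 1/(2n − 4)], with 2n − 3 df.
- Ratio: k²(1 − rho²)/(1 + k² − 2·rho·k) × [1 + 1/(2n − 4)].

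Example, n = 15, k = 1, rho = 0.5: 0.75/1.00 × (1 + 1/26) = 0.779.

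**Variance ratio, ANCOVA/interaction, n = 15**

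| k | rho 0.3 | 0.5 | 0.7 | 0.9 | no gain when rho is |
|---|---|---|---|---|---|
| 0.9 | 0.60 | 0.69 | 0.78 | 0.84 | never |
| 1.0 | 0.68 | 0.78 | 0.88 | 0.99 | above 0.93 |
| 1.1 | 0.74 | 0.85 | 0.96 | 1.04 | 0.79 to 0.96 |
| 1.25 | 0.82 | 0.93 | 1.02 | 0.99 | 0.65 to 0.89 |

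At n = 25 and k = 1.0 the ratios are 0.66/0.77/0.87/0.97.

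**Worst case.** The interaction term minus the ANCOVA term is 1 − 2·rho·k + rho²k² = (1 − rho·k)², which is never negative. ANCOVA can therefore lose only through the factor 1 + 1/(2n − 4): 1/26 = 3.8% at n = 15 and 1/46 = 2.2% at n = 25.

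**Mean 95% CI half-width** (pre-SD units, n = 15, interaction to ANCOVA, rho 0.3/0.5/0.7/0.9):
- k = 1.0: 0.88 to 0.72, 0.74 to 0.65, 0.57 to 0.54, 0.33 to 0.33.
- k = 1.25: 1.00 to 0.90, 0.85 to 0.82, 0.67 to 0.68, 0.41 to 0.41.

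**Power, illustrative only** (noncentral t, effects taken in post-SD units, k = 1, rho 0.5):

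| effect | n per group | interaction | ANCOVA |
|---|---|---|---|
| 0.8416 | 15 | 60% | 71% |
| 0.8416 | 25 | 83% | 91% |
| 1.3605 | 15 | 95% | 98% |

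**Simulation** (30,000 trials per cell, n = 15, k = 1.0): ratios 0.673/0.779/0.884/0.985 at rho 0.3/0.5/0.7/0.9. Type I error was 0.048 to 0.054 for both tests across the settings simulated.

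**The case against.** The strongest reply is that nothing is broken. The interaction is a valid, unbiased test of the second section 2 hypothesis, the study is a pilot, and a statistician is to be consulted. All of that stands and makes this an optional improvement. The deferral leaves room for ANCOVA but does not commit to it, and adjustment is best fixed before data are seen.

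The gain may also be nil. At rho 0.7 it runs from a 12% lower variance (k = 1.0) to 2% higher (k = 1.25), and at rho 0.9 with k = 1.0 it is about 1%. This stands, and is why the full range is shown.

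The power figures are soft. Section 6(e)(vii) does not say how its SMDs were standardized. If 0.8416 were in change-score SDs, interaction power at 15 per group would be 60% at every rho. Fifteen completers out of 25 enrolled also implies 40% dropout (1 − 15/25). Both points stand. The variance ratios do not depend on the SMD scale.

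A reader might infer that ANCOVA should replace the ANOVA outright. The documents do not support that: section 2 also hypothesizes improvement in both groups, and the comparison across time is the only planned test of it.

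**Conclusion.** The point holds as a cheap, optional improvement. At 15 per group with equal SDs, baseline-adjusted ANCOVA cuts the variance of the IMT effect by about 32%, 22%, 12% and 1% at rho 0.3, 0.5, 0.7 and 0.9. If the post-training SD is 25% larger, the changes are an 18% cut, a 7% cut, a 2% rise and a 1% cut. The loss cannot exceed 3.8% at 15 per group or 2.2% at 25. These figures rest on assumed values of rho and k and on randomization as stated in the protocol.

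A reader might infer that the planned analysis is biased, ignores baseline or leaves the trial underpowered. The documents support none of these. Baseline enters through the change score, and if the effect is as large as the cited P_Imax SMD, power is already about 95% at 15 per group (post-SD units, equal SDs, rho 0.5).

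**What to change.** In section 6(e)(v), keep the comparison across the two time points for the hypothesis that both groups improve, keep the sentence on the statistical consultant, and add:

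> For each outcome measured at the initial evaluation, the between-group IMT effect is the difference in the 6-week value estimated by ANCOVA with group and the baseline value of that outcome (derived the same way at both visits), with a 95% confidence interval; this contrast tests the hypothesis of greater improvement with high-intensity IMT.

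The words in parentheses matter because several outcomes have more than one reading per visit. The walk test is done twice ("Then, we will repeat the six-minute walk test to account for learning effect"), grip strength and single limb stance have three trials, and heart rate variability is recorded under several conditions ("Heart rate variability will be recorded during the above 3 outcome measures"). The investigator chooses the derivation. Accelerometer activity is outside this change.

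The cost is one sentence and one residual degree of freedom. It needs no new data and no change to section 2, and it runs in the SPSS software already planned.

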- c) The Physical Therapy program at TWU-Dallas campus has the equipment and the research space needed for this study. The campus is located in an 8-floor building which was opened in 2011 and housed a few health sciences programs such as nursing, occupational therapy, and physical therapy programs. There are several new equipment and research labs in the building for interdisciplinary research related to qualitative and quantitative studies. There is also a counseling clinic with two experienced clinical psychologists who can provide psychological consultation if needed. There are a few AED (automated external defibrillator) available on certain locations of the campus. In addition, across the street of the campus is the St. Paul Hospital, researchers can send the participant there in case he/she requires medical care as a consequence of the Human Research.
- d) The PI will oversee all research activities of the study. There are four DPT graduate students helping with this study involving evaluations, reassessment, data collection, and data analysis. They participate in this project as a requirement of their “Critical Inquiry” courses under the supervision of the PI at the TWU-Dallas campus. They have taken courses related to research methodology and cardiopulmonary physical therapy, and the NIH Human Subjects Protection Training. The PI is an experienced physical therapist whose expertise is in the management of patients with cardiac or/and pulmonary conditions. The research team members are familiar with ECG interpretation and assessment of exercise intolerance. They also had practiced the study protocol a few times to ensure they are skilled in conducting all procedures efficiently and safely. Two of them will conduct the evaluations and the other two research members will conduct the weekly re-assessment. The evaluators will be blinded to the group assignment.

6) Study Design

a) Recruitment Methods

- i) Potential subjects will be identified via medical charts by two research coordinators at the PHD.
- ii) Potential subjects will be approached via one of the two ways: (1) when discharging from the inpatient heart failure unit, the inpatient research coordinator, [name], will talk to potential subjects about the study; or (2) when they return to the outpatient heart failure clinic for follow up, the outpatient research coordinator, [name], will talk to them about the study.

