Effects of a walking program and inspiratory muscle training

- (h) 6-minute walk test on a hallway- first trial: assess subject's physiologic responses closely
 - (i) resting for 15-20 minutes in sitting and completing two surveys
 - (j) 6-minute walk test – 2nd trial : monitor subject's physiologic responses closely
 - (k) give a pedometer, an accelerometer, a breathing device, a heart rate monitor
- (3) exercise training program at home
- (a) for participants :
 - (i) daily walking routine: record daily step counts, duration of breathing exercise, and training target of P_Imax in the log
 - (ii) weekly follow-up for re-assessment of P_Imax at heart failure clinic or at the research participant's home
 - (b) for researchers:
 - (i) ask subjects for any concerns/difficulties during walking program and breathing exercise at weekly follow up: determine whether to continue the study or discontinue
- (4) final evaluations : repeat the same tests as those done during the first visit

iii) Procedures:

The initial evaluation session will last approximately two hours which will include the interview to gather basic demographic and medical data such as names, telephone number, complete address, email address, dates of treatments and birth date, medications, height, weight, age, and past medical history. After the interview, we will measure the maximal inspiratory pressure (P_Imax) that the subject can generate by a pressure threshold spirometer (Micro Direct, Inc. ME 04240), which is directly related to respiratory muscle strength. Then, the individual will be connected with a holter monitor to monitor their heart rate activity.

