- vi) Most of previous similar studies had sample sizes ranging from 20 to 50 each group. So, we plan to screen enough subjects and enroll 30 subjects from the PHD site in one year, excluding screening failure. Other site of the study is the TWU-Dallas campus. Eligible patients can refer themselves to our campus via words by mouth and flyers.

vii) Justification of sample size:

Based on the systematic review on the effects of inspiratory muscle training (IMT) in patients with chronic heart failure by the PI ([name] et al 2012), it showed that patients with CHF demonstrated significant improvements in several outcome measures when compared to control groups after IMT training. The improvements include: (1) functional capacity (1.5422 standardized mean difference (SMD), 95% C.I. with a range of 0.8416 to 3.6553, $p < 0.0001$); (2) P_Imax (1.3605 SMD, 95% C.I. with a range of 1.0510 to 1.6700, $p < 0.0001$); (3) V_{O2} Peak (1.7835 SMD, 95% C.I. with a range of 1.3625 to 2.2046, $p < 0.0001$); (4) Dyspnea (-0.5973 SMD, 95% C.I. with a range of -1.0000 to -0.1946, $p < 0.0037$). The high standardized mean difference (SMD) in all four outcome variables indicates large effect sizes. The low p-values in the four outcome variables indicate the large effect sizes are unlikely due to chance. Based on the large effect size and the power of 80%, a sample size of 15 in each group is determined. Considering potential drop out, we plan to enroll about 25 participants in each group for the whole project.

f) **Provisions to monitor the data for the safety of subjects**

N/A - this study only involves minimal risks to subjects.

g) **Withdrawal of subjects**

Subjects may withdraw at any time without consequences of any kind or loss of benefits to which subjects are otherwise given. If a subject's medical condition got worsen for any reasons and would not benefit from the study, the PI or research staff can stop his/her participation. When a subject drops out from the study, data management will depend on the extent of data has been collected. The PI will consult statistician on this issue at a later stage of the study.

7) Risks to subjects

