- a) Possible risks include fatigue, overexertion, or loss of confidentiality. The fatigue or overexertion could occur during their daily walking program or breathing exercise which will last only a few minutes. Subjects will be advised to judge their tolerance with these exercise, then progress the intensity and duration gradually according to their own tolerance.
- b) Risks such as embarrassment from filling out sensitive questionnaires could happen. If a subject finds any questions in the survey or questionnaire discomfoting, he/she does not have to answer that question.

8) Potential benefits to subjects

Subjects will benefit from free access to the breathing exercise training program and individually tailored walking program. They may improve their exercise tolerance and breathing strength through the study. A free pedometer, a heart rate monitor, and a breathing device will be provided to them for free. Each subject will also receive \$25 at the initial evaluation and another \$25 at the final visit after 6 weeks of home-

based training.

9) Provisions to protect the privacy interests of subjects

The evaluations and weekly follow-up will be conducted in a private room or space where only the participant and research team members are present, except when they are performing the walking tests on a hallway. No other personnel will be allowed in the interview area.

10) Provisions to maintain the confidentiality of data

a) The data will be coded. For example, each participant will be coded as "group number + subject number" (e.g., C-1 refers to control group-subject 1); E-1 refers to experimental group-subject 1). An excel file with the master list linking subjects' initials and codes will be stored in a password protected computer. Only research team members have access to the computer. During most of the data management processes, only the codes will be used.

b) The data will be stored in a locked cabinet in Room 5610 at the School of Physical Therapy of the TWU- Dallas campus. Only the research team members have access to the data. The data will be stored for 10 years after completion of the study and it will be deleted from the computer and hard copies will be shredded after 8/31/2023.

11) Medical care and compensation for injury

N/A - this study only involves minimal risks to research participants

12) Cost to subjects

This walking program and breathing exercise will be free to research participants in the study.

13) Consent process

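### Staff who know the arm can end a participant's participation, with no provision for the 6-week evaluation afterwards, so staff-initiated stops could bias the comparison

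*Combined protocol and SAP*

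**What the plan says.** All references are to the combined protocol and SAP.

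- **Staff-initiated stop, section 6(g).** Where a subject's medical condition "got worsen for any reasons and would not benefit from the study, the PI or research staff can stop his/her participation". The rule is permissive, and it does not define who counts as research staff.
- **Weekly decision, section 6(d)(ii)(3)(b).** At weekly follow-up the researchers ask about concerns or difficulties with the walking and breathing exercises and then "determine whether to continue the study or discontinue". No criterion is given.
- **Who knows the arm, section 6(d)(iii).** "Only the primary investigator and those research members who conduct the weekly re-assessment" of P_Imax know the assignment. Section 5(d) adds: "The evaluators will be blinded to the group assignment".
- **Outcome data.** Section 6(d)(iii): "All the initial outcome evaluations will be repeated after 6 weeks". It neither includes nor excludes people whose participation was stopped. The analysis in section 6(e)(v) is a group-by-time repeated-measures ANOVA with one pre-training and one post-training value. No analysis population or imputation method is named. Section 6(g) leaves the handling of drop-out data to the amount collected and to later statistical advice.
- **Study endpoint, section 6(c)(i).** "The primary study endpoint will be that 30 participants complete all evaluations, reassessment, and 6-week of training program".

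**The concern.** Whether a worsened participant would still benefit is a matter of judgement, and the people identified as making it know the arm. They also know that sham IMT is set at 15% of P_Imax, below the training threshold reported in the literature (section 6(d)(iii)), and that the hypothesis expects more improvement with high-intensity IMT (section 2). Two equally worsened participants in different arms might therefore not be stopped equally often.

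That would matter little if every stopped participant were still measured at 6 weeks. As written, a stop ends participation, and no provision brings the person back. Stopped participants are by definition doing badly. If more of them vanish from one arm, the mean of those who remain in that arm improves for reasons unrelated to training. More stops in the high-intensity arm would flatter high-intensity IMT, and more stops in the sham arm would flatter sham.

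This point covers staff-initiated stops only. The general deferral of drop-out handling is a separate matter.

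**Working it through.** **The plan's own figures.** The documents give no worsening rate, stop rate or bias. The relevant stated figures are 15 per group for 80% power and about 25 per group enrolled (section 6(e)(vii)). The implied loss allowance is (25 − 15)/25 = 40%, and 15/(1 − 0.40) = 25. The figure of 15 can be reached with an SMD of 1.0510, the lower confidence limit for P_Imax, at an assumed two-sided 5% level (15 by the normal approximation, 16 by the t-test). The plan does not say which effect size or level it used.

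**Case 1: stopped participants left out.** Assumptions: n = 25 per arm; w worsen in each arm (2 to 5); they end d SD below the rest (0.5 to 1); m of them are stopped and missing in one arm and none in the other.

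Spurious difference = d × [w/25 − (w − m)/(25 − m)]

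| w | m | d = 0.5 | d = 1 |
|---|---|---|---|
| 2 | 1 | 0.019 | 0.038 |
| 5 | 1 | 0.017 | 0.033 |
| 2 | 2 | 0.040 | 0.080 |
| 5 | 2 | 0.035 | 0.070 |
| 5 | 3 | 0.055 | 0.109 |
| 5 | 4 | 0.076 | 0.152 |
| 5 | 5 | 0.100 | 0.200 |

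With stops in both arms, 3 of 5 v 1 of 5 gives d × (4/24 − 2/22) = 0.038 to 0.076 SD, within the range for a net imbalance of two.

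Scale: the standard error of the difference with 25 per arm is √(2/25) = 0.283 SD. So 0.080/0.283 = 28% and 0.200/0.283 = 71%. Against the cited P_Imax SMD of 1.3605, 0.080 is 6% and 0.200 is 15%.

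Beyond the assumed range, with every worsened participant stopped in one arm and none in the other at d = 1, 7 of 25 gives 7/25 = 0.280 SD and 8 of 25 gives 0.320 SD. One standard error is therefore passed at 8 of 25, a 32% loss, which is inside the 40% allowance.

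**Case 2: stopped participants kept with an imputed value.** This was simulated, and every rate and correlation is an assumption. The change score has SD 1. Staff see a health signal correlated 0.3 to 0.7 with the final change and stop those with the worst signal. Stop rates differ by 10 to 20 percentage points between arms.

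- Left out of the analysis: a shift of about 0.04 to 0.25 SD, in either direction. Equal stop rates give about 0.
- Kept with baseline carried forward (change set to 0), no true effect: still a shift of about 0.03 to 0.20 SD.
- Kept with baseline carried forward, true effect 1.051 SD: the estimate falls short of the effect under continued training by about 0.02 to 0.39 SD. Equal stop rates of 10% or 20% alone give 0.10 × 1.051 = 0.11 or 0.20 × 1.051 = 0.21 SD, which is dilution rather than imbalance.

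The run with no true effect is the cleanest evidence that imputing does not remove the problem.

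**Case 3: stopped participants measured at 6 weeks.** Take w = 5, d = 1 and two stops v none. The residual shift is 0.070 SD if neither attends, 0.033 if one attends and 0 if both attend. The zero refers to the effect of assignment.

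**The case against.** The strongest reply is that nothing shows staff would judge benefit by arm. Section 8 states benefit for everyone: "Subjects will benefit from free access to the breathing exercise training program and individually tailored walking program". Both arms walk. Weekly staff need the arm in order to reset the IMT load, and any trial with unblinded trainers who may halt training shares this feature. This stands in part. The mechanism is a possibility, its direction is unknown, and the research staff in section 6(g) could include blinded evaluators. What remains is that the identified deciders know the arm. That the re-assessors take the weekly decision is an inference, though a sound one, because it falls at the visit they conduct.

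A second reply is that no text says stopped participants are left out, and that the 6-week evaluations are planned without exception. Equally, no text says they return, and section 6(g) stops participation rather than training.

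Third, the remedy has a price: keeping two untreated participants dilutes an SMD of 1.36 by 0.11, more than the 0.08 SD shift from a two-stop imbalance. That is true, but dilution is part of the effect of assignment, so the plan should say that this is the effect it estimates.

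A reader might also infer that the two stop routes conflict, or that a worsening participant expected to benefit cannot be stopped. The documents do not support this. Section 6(g) says what staff can do, not the only ground for acting; the weekly check is a general one; and subjects may withdraw at any time. The difference is one of wording.

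**Conclusion.** The point holds as a minor one, with medium confidence. Stops by staff who know the arm could differ between arms, and as written a stop can cost the 6-week value.

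Under the assumptions above (25 per arm, 2 to 5 worsening per arm by 0.5 to 1 SD, stopped participants left out), the shift is about 0.02 to 0.08 SD for a net imbalance of one or two stops. It reaches 0.20 SD, 71% of a standard error, in the extreme of 5 v 0, which no text suggests will happen.

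Three firmer readings are tempting and go too far:

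- *The bias favours high-intensity IMT.* The direction cannot be told from the documents.
- *The bias is certainly small.* That depends on rates the documents do not give.
- *The bias arises only if stopped participants are excluded.* Carrying baseline forward can also bias the comparison, and arm-aware stops alter the treatment received even when data are complete.

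**What to change.** 1. Reword section 6(g), and the weekly decision in section 6(d)(ii)(3)(b), so that a staff-initiated stop ends training only.
2. Invite every stopped participant to the already planned blinded 6-week evaluation where it is safe. If the walk tests are unsafe, collect the two questionnaires alone.
3. Analyse stopped participants in their assigned group, and state that the estimate is the effect of assignment (intention-to-treat).
4. Record the reason for and initiator of each stop, and report stops by arm.

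Removing the benefit clause from section 6(g) and naming the research staff are optional tidying. Removing the clause alone would widen unblinded discretion, so it should be done only together with items 1 to 4.

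**Cost.** Wording changes, two form fields, and a final visit for a few people; that visit and its $25 payment are already planned (section 8). No new staff are needed. The estimate is diluted somewhat: if 2 of 25 high-intensity participants gain nothing, 1.3605 × 23/25 = 1.25. Power at 25 per arm (two-sided 5% t-test, level assumed) goes from 0.997 to 0.991. At an assumed SMD of 0.8 the effect becomes 0.736 and power goes from 0.79 to 0.72, against 0.77 if the two were excluded. Stopped participants still count as not having completed training under section 6(c)(i).

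**Limit.** Unblinded staff keep their discretion over stopping training, and those who do not attend at 6 weeks remain missing.
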